15.7.2. DiseaseResponse Endpoints

- PSA response according to the PCWG3 criteria:
 - Only subjects who have a baseline PSA value and at least one post-baseline assessment will be included in the analysis of PSA response.
 - PSA Response Rate is defined as proportion of subjects with a decrease of $\geq 50\%$ in the PSA concentration from the baseline PSA value determined at least 9 weeks after start of treatment and confirmed after ≥ 4 weeks by an additional PSA evaluation.
- Radiographic response By Recist 1.1 for subjects with measurable disease (Appendix 5)

References

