3.3.7. Part 1: Futility and Efficacy Analysis for GCB-DLBCL Subjects

There will be a GCB-DLBCL expansion cohort enrolled after the completion of dose escalation in Part 1. For the GCB-DLBCL expansion cohort in Part 1, futility and efficacy evaluation of overall response data will be performed in order to support the early decision regarding opening Part 2 dose expansion. The methodology is based on the Bayesian predictive probability of success if enrollment continues until all planned subjects are recruited [[Lee, 2008](#)]. Details of the predictive probability methodology, futility and efficacy evaluation are explained in Section 12.2.1.2. In summary, a minimum of 13 and maximum of 27 GCB-DLBCL patients will be enrolled. Once 13 GCB-DLBCL patients at MTD/RP2D have been enrolled (including patients in dose escalation phase) and have completed response assessments of safety and efficacy, response data will be reviewed on an ongoing basis for evidence of futility or efficacy.

For futility/efficacy analysis, subjects evaluable for response assessment will be defined by any or all of the following criteria:

- Subjects who have at least two post-baseline radiological disease assessments and have been on study for at least 28 days (one cycle)
- Subjects who have progressed or have died or have withdrawn from study treatment due to any reason.

Interim analysis (IA) of futility and efficacy can be conducted at any time after 13 GCB-DLBCL subjects have enrolled and are evaluable for response assessment. If the thresholds for futility are met, the Part 1 expansion cohort may be stopped based upon the evaluation of the totality of the data. If the efficacy thresholds are reached, then Part 2 expansion may be opened. If neither futility nor efficacy thresholds are met at any interim analysis, and the totality of the data does not support continuation of the trial, then the trial may be terminated. All available data will be considered in making decision of termination or continuation of the trial.

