5. STUDY POPULATION

5.1. Number of Subjects

A maximum of approximately 250 subjects will be enrolled. See Section [12.2](#) for sample size assumptions.

The number of dose levels and the level at which the RP2D [or maximum tolerated dose (MTD) or maximum feasible dose (MFD)] is reached cannot be determined in advance. An adequate number of subjects will be enrolled into the study to establish the recommended dose(s) for further study. It is estimated that approximately 40 subjects will be enrolled into Part 1 dose-escalation of the study. Additionally in Part 1 cohort expansion, approximately 27 GCB-DLBCL subjects and approximately 15 solid tumor subjects containing EZH2 inhibitor sensitizing mutations or subjects with prostate cancer will be enrolled.

Approximately up to 168 subjects will be enrolled in Part 2 in five expansion cohorts: two GCB-DLBCL cohorts with up to 32 subjects from the EZH2 wild-type population, and up to 32 subjects from the EZH2 mutation positive population, and two tFL cohorts with up to 32 subjects from the EZH2 wild-type population and up to 32 subjects from the EZH2 mutation positive population and up to 40 subjects in the MM cohort. Additional subjects/cohorts may be enrolled to allow for evaluation of additional dose levels.

In Part 1 (dose-escalation) of the study, if subjects prematurely discontinue, additional subjects may be enrolled and assigned to the same treatment sequence at the discretion of the Sponsor in consultation with the investigator. Subjects will not be replaced in Part 2 (expansion cohort) of the study.

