6.3. Permanent Discontinuation from Study Treatment

Subjects will receive study treatment until disease progression, death or unacceptable toxicity, including meeting stopping criteria for liver chemistry defined in Section [8.3.1](#). In addition, study treatment will be permanently discontinued for any of the following reasons:

- Substantial deviation(s) from the protocol
- Request of the subject or proxy (withdrawal of consent by subject or proxy)
- Investigator's discretion
- A dose delay of >21days unless the investigator and GSK Medical Monitor agree that further treatment may benefit the subject
- Intercurrent illness that prevents further administration of study treatment(s)
- Subject is lost to follow-up
- Study is closed or terminated
- Female subject who becomes pregnant while on study treatment

The primary reason study treatment was permanently discontinued must be documented in the subject's medical records and eCRF.

If the subject voluntarily discontinues from treatment due to toxicity, 'adverse event' will be recorded as the primary reason for permanently discontinuation on the eCRF.

Once a subject has permanently discontinued from study treatment, the subject will not be allowed to be retreated.

All subjects who discontinue from study treatment will have safety/disease assessments at the post study treatment Follow Up Visit as specified in the Time and Events Tables.

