	STUDY PHASE	SCREEN	First Treatment Period Cycle 1			Day 21	Continuation Phase Cycle 2 and beyond	Follow-Up^j
			Day 1 and 4^a	Day 8 and 11^a	Day 15 and 18^a			
	VISIT	VISIT WINDOW (±days)					±7^l	±7^l
SPEP, FLC assay, quantitative immunoglobulins (IgG, IgA, IgM)	Not required for subjects with non-secretory MM	X					X	
UPEP	Only required if paraprotein is present in urine	X						
Extramedullary Disease Assessment	Only required for MM with extramedullary disease	X						
BM aspirate and biopsy	Required for non-secretory MM, or as appropriate for other subjects	X			Day 18		Week 10, Day 1	
Disease Assessments for Solid Tumors: Baseline disease assessments at screening and repeated every 8 weeks after dosing is initiated								
CT/ Magnetic Resonance Imaging (MRI) ^k	Must be completed within 4 weeks of first dose of GSK2816126 and repeated every 8 weeks	X					X ^d	X ^d

	STUDY PHASE	SCREEN	First Treatment Period Cycle 1			Day 21	Continuation Phase Cycle 2 and beyond	Follow-Up^j
			Day 1 and 4^a	Day 8 and 11^a	Day 15 and 18^a			
	VISIT	Screen						
	VISIT WINDOW (\pmdays)	-14					$\pm 7^l$	$\pm 7^l$
Positron emission tomography (PET)	The use of standalone PET or PET in combination with CT scan is optional. Standalone PET does not replace CT	X ^e					X ^{d, e}	X ^{d, e}
Disease Assessments for Prostate Cancer: (in addition to those assessments for all solid tumor subjects): Baseline disease assessments at screening and repeated as noted below after dosing is initiated								
PSA	Wk 9 and every 4 weeks thereafter	X					X	X
Study Medication								
GSK2816126 Dosing ^a	Dosed 2x weekly with at least 2-3 non-dosing days in between dosing days (3 weeks on/1 week off)							

- a. A subject is to receive two doses per week which should be given with at least 2 non-dosing days in between on the same day of the week during Cycle 1.- If there is a need to change scheduling after Cycle 1, the scheduled days of the week can change as long as there are 2-3non-dosing days between dosing days.

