- b. Timings for triplicate in-house on-drug ECGs are pre-infusion, at the end of infusion, before bed, and before discharge the next morning for Day 1 of cycle 1 only. Other protocol-mandated ECGs should be performed in triplicate pre-infusion and at the end of infusion (Section 7.3.4). Two copies of the ECG tracing should be obtained at the time of the ECG, one to be kept in the study file for retrospective collection by the sponsor if necessary. ECG data should be reviewed by qualified personnel with experience in this study population
- c. Retention of screen-failure tumor tissue: all or a portion of archival or fresh biopsy tissue from screen-failure subjects, used for central testing of GCB-DLBCL or EZH2 mutation status, will be retained. This tissue may be used in the validation of potential diagnostic assays to detect EZH2 mutations and/or for GCB-DLBCL subtyping.
- d. If the Follow-up visit \geq 8weeks from the previous response scan time point, scans should be obtained to confirm/ evaluate response.
- e. Standalone PET dose not replace CT. Diagnostic CT is the preferred method of disease assessment. PET/CT may be used as an alternative at the investigator's discretion.

- f. Only if initially and/or previously positive & required for CR or as clinically indicated.
- g. Whole Blood for Biomarker sample at Cycle 2 day 1 must be taken prior to start of dosing.
- h. If tissue sample not able to be taken at C1D18, site should discuss with GSK regarding having the sample taken at the next possible Cycle visit
- i. Serum beta-human chorionic gonadotropin (B-HCG) pregnancy test
- j. Follow up visit should be performed 30 days from last dose of study medication
- k. Baseline brain scans are required for all subjects. Thereafter brain scans should be conducted as clinically indicated. Bone scans are to be conducted as clinically indicated at baseline and subsequent follow up timepoints. Subjects undergoing baseline full body CT/PET will not require this additional scans, unless clinically indicated.
- l. After Cycle 1, assessments that are conducted at less frequent intervals (i.e., every 8 weeks) will have a visit window of \pm 7 days after Cycle 1
- m. Part 2 subjects enrolled into the PK/PD cohort will have these assessments performed in addition to all other study assessments included in the Time and Events table

Table 7 Time and Events, PK Sampling Table for Part 1, Day 1 and Day 15

	Duration of Infusion in hours		
	2	3	4

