12.3.1. Analysis Populations

All Subjects Population: This will consist of all subjects who received at least one dose of study treatment. Safety and clinical activity analyses will be evaluated based on this population.

The PK Concentration Population: This will consist of those subjects in All Subjects Population for whom a PK sample is obtained and analyzed.

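### The PSA response rate leaves out treated subjects with no post-baseline assessment, which conflicts with the all-treated population and can only push a non-zero rate upward

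*Protocol*

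**What the plan says.** Protocol section 15.7.2 (Appendix 7) fixes who counts towards PSA response: "Only subjects who have a baseline PSA value and at least one post-baseline assessment will be included in the analysis of PSA response". The same section defines a responder by a fall of at least 50% from baseline, "determined at least 9 weeks after start of treatment and confirmed after ≥ 4 weeks by an additional PSA evaluation".

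Section 12.3.1 defines the All Subjects Population by receipt of at least one dose and adds: "Safety and clinical activity analyses will be evaluated based on this population".

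The PSA row of the Time and Events Table (section 7.1, Table 6) has a screening PSA and then "Wk 9 and every 4 weeks thereafter". It also has an entry in the Follow-Up column. A footnote to that table gives the timing: "Follow up visit should be performed 30 days from last dose of study medication". Section 6.3 says who attends: "All subjects who discontinue from study treatment will have safety/disease assessments at the post study treatment Follow Up Visit as specified".

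For the GCB-DLBCL futility and efficacy analysis, section 3.3.7 treats as evaluable "Subjects who have progressed or have died or have withdrawn from study treatment due to any reason". No such provision is written for PSA response.

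**The concern.** A treated subject with no post-baseline value is not a missing observation of unknown sign. Under the protocol's own definition, that subject cannot be a responder. Removing such subjects makes the denominator depend on what happened after treatment began, and death or withdrawal soon after starting is plausibly related to lack of benefit.

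Clinical activity in prostate cancer is part of a Part 1 secondary objective (section 2.1). CRPC subjects may enter on a PSA of at least 5 ng/mL without RECIST-measurable disease (section 5.2.1), and section 15.7.2 limits radiographic response to subjects with measurable disease. For the PSA-only entrants, PSA is the only response measure. The group is small: section 5.1 says that "approximately 15 solid tumor subjects containing EZH2 inhibitor sensitizing mutations or subjects with prostate cancer will be enrolled", and does not say how many of these will have prostate cancer. One or two exclusions would be visible in the reported percentage.

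**Working it through.** The protocol gives no expected PSA response rate, target or PSA-based sample size, so there is no stated figure to reproduce. The check has three steps.

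**1. Who can drop out.** Screening PSA is followed by week 9 on treatment. A subject who stops earlier is due a PSA at follow-up. For example, a last dose on Day 18 of cycle 1 puts that visit at about day 18 + 30 = 48, or week 7. A subject who attends has a post-baseline PSA and stays in the denominator as a non-responder. Those who drop out die, withdraw consent, are lost, or miss the follow-up visit before any post-baseline PSA.

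**2. Direction.** The earliest confirmed response is at about week 9 + 4 = week 13 and needs two post-baseline PSA values. A subject with none is a non-responder. Let N be the treated subjects with a baseline PSA, r the confirmed responders and k the number with no post-baseline PSA.

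- All-treated rate: r/N
- Rate under section 15.7.2: r/(N-k)
- Ratio: N/(N-k) = 1/(1-m), with m = k/N

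The ratio exceeds 1 whenever k > 0, so a non-zero rate can only rise.

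**3. Size.** N, r and k are assumptions, because the documents give none of them.

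| N | r | All treated | k = 1 | k = 2 |
|---|---|---|---|---|
| 5 | 1 | 20.0% | 1/4 = 25.0% | 1/3 = 33.3% |
| 10 | 2 | 20.0% | 2/9 = 22.2% | 2/8 = 25.0% |
| 15 | 3 | 20.0% | 3/14 = 21.4% | 3/13 = 23.1% |

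The follow-up PSA matters a great deal. Write m = d(1-c), where d is the share stopping before week 9 and c is the share of those who have a follow-up PSA. With an assumed all-treated rate of 20%, the expected rate is 0.20/(1 - d(1-c)):

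| d | c = 0 | c = 0.5 | c = 0.8 | c = 1 |
|---|---|---|---|---|
| 20% | 25.0% | 22.2% | 20.8% | 20.0% |
| 30% | 28.6% | 23.5% | 21.3% | 20.0% |

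The bias vanishes if every early stopper has the follow-up PSA and is largest if none does.

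**The case against.** A reader who sees only the week 9 entry might infer that everyone who progresses or stops for toxicity before week 9 vanishes from the analysis. An early loss of 20% to 40% would then inflate the rate by 1/(1-0.2) = 1.25 to 1/(1-0.4) = 1.67. The documents do not support that. The PSA row also schedules a follow-up PSA, and section 6.3 applies that visit to all who discontinue. Those factors are an upper bound, reached only if no early stopper attends.

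Exits for progression before week 9 should also be few. Section 15.7.1 determines PSA progression no earlier than 9 weeks and does not make it, on its own, a reason to stop. The first scheduled imaging is at week 8. These points limit m, but they do not cover death, withdrawal of consent or loss to follow-up.

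It can also be said that little hangs on the rate. Section 12.1.1 makes the solid tumor expansion descriptive, the listed Part 1 activity endpoint is CR plus PR, and no stopping table uses PSA. PSA-only entrants also contribute to progression endpoints. All of this stands, and it limits the weight of the point.

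Lastly, section 15.7.2 speaks of a post-baseline assessment without expressly saying PSA. A broader reading excludes fewer subjects. Anyone still excluded has no post-baseline PSA either, so the direction is unchanged.

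**Conclusion.** The point holds in a limited form. Sections 15.7.2 and 12.3.1 give different denominators for the same rate, and the narrower one removes only non-responders. The upward direction follows from the response definition and needs no assumption beyond a non-zero rate and at least one exclusion. The size rests on m, which is unknown. In the assumed group of 10 with 2 responders, one or two exclusions add 2.2 or 5.0 percentage points. If follow-up attendance is near complete, the effect is close to nil. It should not be read as showing that early failure alone removes a subject. Because the endpoint is descriptive and drives no decision, this is a worthwhile correction to a stated rule and does not threaten the trial's conclusions.

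**What to change.** In section 15.7.2, make the denominator all treated CRPC subjects with a baseline PSA. Count as a non-responder anyone without a confirmed decline of at least 50%, including subjects with no post-baseline PSA. State the number of treated CRPC subjects without a baseline PSA. A percentage change cannot be computed for them, and reporting the count makes the remaining difference from the section 12.3.1 population explicit. Keep the rate among PSA-evaluable subjects as supportive only, with the number excluded and the reasons.

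The cost is a short text change and possibly a slightly lower reported rate. No new visits, samples or subjects are needed.

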15.8. Appendix 8: Genetic Research

Genetic Research Objectives and Analyses

The objectives of the genetic research are to investigate the relationship between genetic variants and:

- Response to medicine, including GSK2816126† or any concomitant medicines;
- Disease susceptibility, severity, and progression and related conditions

Genetic data may be generated while the clinical study is underway or following completion of the study. Genetic evaluations may include focused candidate gene approaches and/or examination of a large number of genetic variants throughout the genome (whole genome analyses). Genetic analyses will utilize data collected in the clinical study and will be limited to understanding the objectives highlighted above. Analyses may be performed using data from multiple clinical studies to investigate these research objectives.

Appropriate descriptive and/or statistical analysis methods will be used. A detailed description of any planned analyses will be documented in a Reporting and Analysis Plan (RAP) prior to initiation of the analysis. Planned analyses and results of genetic investigations will be reported either as part of the clinical RAP and study report, or in a separate genetics RAP and report, as appropriate.

Study Population

Any subject who is enrolled in the clinical study can participate in genetic research. Any subject who has received an allogeneic bone marrow transplant must be excluded from the genetic research.

Study Assessments and Procedures

A key component of successful genetic research is the collection of samples during clinical studies. Collection of samples, even when no *a priori* hypothesis has been identified, may enable future genetic analyses to be conducted to help understand variability in disease and medicine response.

- A 6 ml blood sample will be taken for Deoxyribonucleic acid (DNA) extraction. Blood sample is collected at the baseline visit, after the subject has been randomized and provided informed consent for genetic research. If a subject initially declines to participate in genetic research and then changes their mind, a sample should be obtained at the earliest opportunity. Instructions for collection and shipping of the genetic sample are described in the laboratory manual. The DNA from the blood sample may undergo quality control analyses to confirm the integrity of the sample. If there are concerns regarding the quality of the sample, then the sample may be destroyed. The blood sample is taken on a single occasion unless a duplicate sample is required due to inability to utilize the original sample.

The genetic sample is labelled (or “coded”) with the same study specific number as used to label other samples and data in the study. This number can be traced or linked back to the subject by the investigator or site staff. Coded samples do not carry personal identifiers (such as name or social security number).

Samples will be stored securely and may be kept for up to 15 years after the last subject completes the study or GSK may destroy the samples sooner. GSK or those working with GSK (for example, other researchers) will only use samples collected from the study for the purpose stated in this protocol and in the informed consent form. Samples may be used as part of the development of a companion diagnostic to support the GSK medicinal product.

Subjects can request their sample to be destroyed at any time.

Informed Consent

Subjects who do not wish to participate in the genetic research may still participate in the clinical study. Genetic informed consent must be obtained prior to any blood being taken for genetic analysis.

Subject Withdrawal from Study

If a subject who has consented to participate in genetic research withdraws from the clinical study for any reason other than being lost to follow-up, the subject will be given a choice of one of the following options concerning the genetic sample, if already collected:

- Continue to participate in the genetic research in which case the genetic DNA sample is retained
- Discontinue participation in the genetic research and destroy the genetic DNA sample

If a subject withdraws consent for genetic research or requests sample destruction for any reason, the investigator must complete the appropriate documentation to request sample destruction within the timeframe specified by GSK and maintain the documentation in the site study records.

Genotype data may be generated during the clinical study or after completion of the clinical study and may be analyzed during the clinical study or stored for future analysis.

- If a subject withdraws consent for genetic research and genotype data has not been analyzed, it will not be analyzed or used for future research.
- Genetic data that has been analyzed at the time of withdrawn consent will continue to be stored and used, as appropriate.

Screen and Baseline Failures

If a sample for genetic research has been collected and it is determined that the subject does not meet the entry criteria for participation in the clinical study, then the investigator should instruct the participant that their genetic sample will be destroyed. No forms are required to complete this process as it will be completed as part of the consent and sample reconciliation process. In this instance a sample destruction form will not be available to include in the site files.

Provision of Study Results and Confidentiality of Subject's Data

GSK may summarize the genetic research results in the clinical study report, or separately and may publish the results in scientific journals.

GSK may share genetic research data 'with other scientists to further scientific understanding in alignment with the informed consent. GSK does not inform the subject, family members, insurers, or employers of individual genotyping results that are not known to be relevant to the subject's medical care at the time of the study, unless required by law. This is due to the fact that the information generated from genetic studies is generally preliminary in nature, and therefore the significance and scientific validity of the results are undetermined. Further, data generated in a research laboratory may not meet regulatory requirements for inclusion in clinical care.

